2.1. Aims

There are three overall aims of the CRAFT project which correspond to each distinct part:

- i. To understand the association between the degree of cervical dilatation at CS in labour with risk of LM/PTB in subsequent pregnancies.
- ii. To assess the efficacy of cervical cerclage for a short cervix ≤ 25 mm detected by transvaginal ultrasound in a randomised controlled trial of women with previous FDCS (CRAFT-RCT).
- iii. To identify a mechanism for the increased risk of preterm birth with MRI and transvaginal ultrasound in order to predict those at most risk and whether cervical cerclage would be of benefit (CRAFT-IMG)

2.2. Study objectives

2.2.1. CRAFT-OBS: a study of risk and management in women with a history of CS in labour

- i. Determine the incidence of LM and PTB (prior to 37 weeks) in women with previous CS in labour stratified by cervical dilatation.

- ii. If ultrasound measured cervical length and quantitative fibronectin are carried out, this data will be collated and help evaluate the ability of these tests to determine risk of preterm birth in women with a history of in labour caesarean.

2.2.2. CRAFT-RCT: a trial of USS indicated cerclage in women with history of FDCS

- i. Determine if an ultrasound-indicated cervical cerclage is effective management in women with a history of FDCS and cervical shortening (<25 mm) in preventing LM or PTB <34 weeks gestation. Evaluate the impact of intervention on short-term fetal and neonatal outcomes, assessed as a composite of fetal and perinatal death and major morbidity.
- ii. Assess the impact of both management strategies (i.e. cerclage and observation) on health economic outcomes for mother and infant in terms of number of nights in hospital; cost data to hospital discharge/28 days post delivery.

2.2.3. CRAFT-IMG: a sub-study evaluating imaging methods for assessing risk and management of women with a history of FDCS

- i. Ascertain whether MRI or ultrasound (or a combination of the two) can accurately predict PTB when abnormalities are detected in the cervix.
- ii. Identify which women are most likely to benefit from intervention.

3. Study Design

3.1. CRAFT-OBS

This is a multicentre prospective cohort observational study of 2200 pregnant women with a previous history of CS in labour who will be recruited following their booking or scanning visit (Appendix: participating sites). Women who have had a previous FDCS and who are found to have a CL \leq 25mm on transvaginal ultrasound will be offered recruitment to the CRAFT-RCT (see below). Women with a previous FDCS and a CL \geq 25mm may be invited to participate in CRAFT-IMG. If patients have a clinically indicated transvaginal cervical length or qfFN during their pregnancy, this information will also be collected.

3.2. CRAFT-RCT

This is a multicentre randomised controlled trial (RCT), carried out over 27 months in at least 41 hospitals performing surveillance (n=1000). All women with a history of FDCS will have CL

monitoring as per new guidance <24 weeks(1). If their cervical length is or becomes <25 mm they will be randomised (1:1) into one of two groups:

- cervical cerclage plus standard management
- standard management

3.3. CRAFT-IMG

This is a prospective cohort sub-study collecting image data and outcomes in a sub-group of women participating in CRAFT-OBS (n=30) and CRAFT-RCT (n=30).

The subgroup will be recruited from participants attending University College London and St Thomas' Hospital only. All participants will have experienced FDCS in a previous pregnancy and will include women with and without cervical shortening in the current pregnancy based on their CL monitoring. Participants will be allocated to one of three groups: a) women with cervical length of <25 mm who have been randomised to cerclage in CRAFT-RCT (n=15), b) women with cervical length of <25 mm who have been randomised to observation in CRAFT-RCT (n=15), c) women with cervical length of ≥ 25 mm.

A transvaginal ultrasound using a new enhanced protocol developed by [name] at UCL will be undertaken in all women. This procedure is more detailed than standard measurement of CL. The site of previous scar tissue and any other abnormalities (for example the presence of cysts) will be recorded. Serial MRIs will also be performed. Recruited patients will have up to 3 serial transvaginal ultrasounds and MRIs during their pregnancy.

3.4. Expected study duration

Recruitment will be conducted over a 24 month period. The end of the study will be defined as 28 days post-delivery or discharge from hospital (whichever sooner) of the last recruited participant and infant. Women will be followed-up until postnatal discharge. The end of the study will be reported to the REC and Regulatory Authority within 90 days, or 15 days if the study is terminated prematurely.

4. Study Endpoints

4.1. CRAFT-OBS

Primary endpoint:

- i) Delivery < 37 completed weeks gestation (powered).

Secondary endpoints

- i) Adverse perinatal outcome, defined as a composite outcome of death (ante-partum/intra-partum stillbirths plus neonatal deaths prior to discharge from neonatal services)
- ii) Delivery <34 weeks gestation.
- iii) Gestation at delivery.
- iv) Late miscarriage (14⁺⁰-23⁺⁶ weeks).
- v) Healthcare use, e.g. appointments, hospital admission, cervical length, cervicovaginal fetal fibronectin levels, interventions.
- vi) Predictive modelling to evaluate the ability of CL and fFN to determine risk of preterm birth <34 and <37 weeks
- vii) Other maternal and fetal morbidities, as per COPOP core outcome set for preterm birth intervention studies(15).

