4.3. CRAFT-IMG

Primary endpoint:

- i. Alterations in imaging parameters between women with a full dilatation C-section in a previous pregnancy and either a cervix $\leq 25\text{mm}$ or a cervix $>25\text{mm}$ in this pregnancy which culminates in a preterm (<37 week) delivery.

5. Sample size and power calculation

All power calculations were performed by the trial statistician [name].

CRAFT-OBS: With estimated prevalence of 15% preterm birth rate prior to 37 weeks, and 16.2% of all deliveries being by emergency caesarean section; we will require data on 2200 women to estimate the event rate to 10% relative accuracy (e.g. 13.5% to 15.6%).

An average district general hospital has 4,000 deliveries per year, of which 648 (16.2%) might be by Emergency Caesarean. We aim to recruit 324 of these (50%) at a minimum of 7 study sites. At St Thomas' Hospital rather fewer deliveries (11%) are caesareans in labour; so we will aim for at least 20 sites, taking the assumptions above into account.

If we acquire data of cervical length and/or quantitative fetal fibronectin in this cohort, we will be able to validate these prediction tools. If we treat a short cervix of $\leq 25\text{mm}$, and a raised qfFN of $\geq 50\text{ng/ml}$ as positive tests, we anticipate a 75% sensitivity and 83% specificity from the literature for both tests (16).

Assuming 10% event rate, 1000 women (100 cases and 900 controls) would allow use to estimate the sensitivities of qfFN and CL to within 10% and the specificities to within 3% of the true value. The PPV would be estimated within 7% and NPV within 1.5% of their true values.

CRAFT-RCT: Pilot data indicates that at least 10% of all births and 70% of preterm births associated with FDCS occur before 34 weeks. In order to detect a reduction in this rate from 10% to 5% 474 women are required in each group to give 80% power. We will aim to recruit 500 in each arm in order to allow for 5% loss to follow-up.

CRAFT-IMG: We consider that the participation of 60 women in this sub-study will provide useful information for planning future research; this is achievable by recruiting at 2 sites (UCLH and St Thomas' Hospital): 30 women with cervix $>25\text{mm}$ and 30 women with cervix $\leq 25\text{mm}$ (15 women with cerclage, 15 women without).

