6.1. Inclusion and exclusion criteria for ALL CRAFT participants

Inclusion criteria:

- Pregnant women under 23⁺⁶ weeks gestation with a history of previous caesarean section in labour.
- Singleton pregnancy.
- Willing and able to give informed consent (with or without interpreter).

Exclusion criteria:

- Under 16 years of age.
- Inability to give informed consent.
- Previous caesarean section carried out before labour.
- Women who have been commenced on management with progesterone, a cerclage or arabin pessary as part of their care or another research study

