7.3. Data Collection

Following consent, data on the participant's demographic characteristics, risk factors, medical and obstetric history will be documented and entered onto the study specific database. This will include current and previous monitoring procedures and/or pregnancy interventions (e.g. cervical length measurements and cerclage). Cervical length will be measured with transvaginal

Study Protocol: **Cerclage After Full-dilatation caesarean-section**

IRAS ID:261294

REC: REC 19/LO/1270

Version 2.0

Date: 10.09.19

ultrasound in accordance with local protocols, measurements will be taken in triplicate and the shortest measurement used. Their pregnancy and neonatal outcomes will be collected from NHS patient records postnatally.

Participants with a history of FDCS will be referred to a preterm surveillance clinic where they will be invited for cervical length assessment (with or without other tests, such as fetal fibronectin) from 14+0 to 23+6 weeks gestation. Cervical length will be measured with transvaginal ultrasound in accordance with local protocols, measurements will be taken in triplicate and the shortest measurement used. If their cervical length is, or becomes ≤ 25 mm during this period they will be offered the opportunity to participate in CRAFT-RCT. Further explanation and a separate information sheet will be provided and additional consent form will be completed and stored as those for the main study. If the participant is unwilling to participate in this randomised controlled trial she will continue to be monitored and cared for as per local protocol/clinicians' experience, and continue in the observation arm of CRAFT study. Outcome data will be collected after the birth of her baby. Women who provide written informed consent will be randomised to either cervical cerclage or standard care.

Sixty participants, recruited at St Thomas' and UCLH, will be invited to have additional imaging tests for the sub-study, CRAFT-IMG. They will be given additional information and asked to sign another consent form, which will be stored as described above. These additional tests will involve serial transvaginal ultrasound measurements of cervical length and macro/microstructural changes as per [name] protocol and MRI scans of macro/microstructural cervical change.

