Participants of the imaging sub-study (CRAFT-IMG) will have a minimum of 1 advanced transvaginal ultrasound and 1 MRI up to a maximum of 3 MRIs and 3 advanced protocol transvaginal ultrasound scans (around 5 minutes longer than a cervical surveillance transvaginal ultrasound). The number carried out depends on the length of the pregnancy and patient’s availability. Where possible these will be co-ordinated with clinical appointments to minimise disruption. Participants will be offered reasonable reimbursement for their travel for these additional appointments.

8. Data analysis

CRAFT-OBS: This study will calculate prediction of preterm birth <37 weeks gestation in women with a previous CS in labour by observing clinical pregnancy outcomes. Where data is available the predictive value based on cervical length and quantitative fetal fibronectin will also be assessed. Results will be presented as both odds ratios and risk differences. Standard predictive statistics will be used for prediction of delivery <34 and <37 weeks gestation.

CRAFT-RCT: CRAFT-RCT: Statistical analysis of results will be undertaken by the research team and [name]. The primary analyses will be by intention to treat. The main outcome is delivery under 34 weeks. Secondary analyses will include secondary endpoints as per section 4.2. Standard predictive statistics will be used for prediction of delivery <34 weeks gestation (cervix ≤ 25 mm will be calculated along with area under the curve). We will also validate our current predictive tools of cervical length and fetal fibronectin in this population. Results will be presented as both odds ratios and risk differences, leading to number needed to treat (NNT) if appropriate, according to CONSORT guidelines. A subgroup analysis will be carried out according to other risk factors for preterm birth other than FDCS.

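### In CRAFT-OBS a cervix ≤25 mm after full-dilatation caesarean is both the positive test and the trigger for randomised cerclage, and the plan has no rule for the treatment that follows

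*Combined protocol and SAP*

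**What the plan says.** Section 4.1, secondary endpoint (vi), is "Predictive modelling to evaluate the ability of CL and fFN to determine risk of preterm birth <34 and <37 weeks". Section 8 adds for CRAFT-OBS: "Where data is available the predictive value based on cervical length and quantitative fetal fibronectin will also be assessed". Section 5 defines a positive cervical-length (CL) test as ≤25 mm. Objective 2.2.1(i) asks for preterm birth incidence by dilatation at the earlier caesarean.

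The same threshold is the entry criterion for CRAFT-RCT (section 6.2), which draws its women from OBS (section 7.1). Section 7.3 refers FDCS women for surveillance and says that if the length is, "or becomes ≤ 25 mm during this period they will be offered the opportunity to participate in CRAFT-RCT". Section 7.4 then allocates 1:1 to cerclage or surveillance. Women who decline are managed locally "and continue in the observation arm of CRAFT study"; nothing equivalent is said of women who accept.

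Treatment is dealt with only at entry, where section 6.1 excludes "Women who have been commenced on management with progesterone, a cerclage or arabin pessary as part of their care or another research study". Sections 4.1, 5 and 8 contain no restriction, censoring, weighting or adjustment for treatment started after the CL measurement.

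**The concern.** The result being evaluated sets off a treatment intended to prevent the outcome it is evaluated against. If that treatment works, some women who would have been true positives deliver later and are counted as false positives. The test then looks worse than it is, and more so the better cerclage works.

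This matters because the Lay and Professional Summaries say it is unknown whether ≤25 mm is a suitable cut-off in these women. OBS has to answer that, since every woman in the RCT is already at or below the threshold. The dilatation comparison is exposed too: trial cerclage is confined to the FDCS group, so an effective cerclage narrows its difference from the 4-9 cm group. Whether randomised women belong to the OBS analysis set also changes the answer, and the plan leaves it open.

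**Working it through.** **1. The plan's own figures (section 5), assuming 95% intervals and two-sided 5% tests.**
- OBS size: 1.96² × 0.15 × 0.85 / 0.015² = 2177, against 2200 stated. This reproduces; the half-width at 2200 is 1.49 points. (Ten per cent either side of 15% is 13.5% to 16.5%, so the printed upper limit of 15.6% looks like a slip; the sample size is unaffected.)
- Accuracy: 1000 women, 100 cases, 900 controls, sensitivity 75%, specificity 83%. This gives TP 75, FN 25, FP 153, TN 747; PPV 75/228 = 32.9%; NPV 747/772 = 96.8%.
- Half-widths (Wald / largest exact, in points): sensitivity 8.5 / 9.7, specificity 2.5 / 2.6, PPV 6.1 / 6.5, NPV 1.2 / 1.5. These agree with the stated 10, 3, 7 and 1.5.
- RCT: 10% v 5% at 80% power needs 474 per arm with continuity correction, as stated. I read the planned effect as a relative risk (RR) of 0.5.

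**2. Randomised women kept in OBS, nothing done about cerclage.** Let c be the share of test-positives given cerclage. Events averted are a = 75 × c × (1 − RR). They move from TP to FP; FN and TN do not change.

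| Case | a | Sensitivity | Specificity | PPV | Event rate |
|---|---|---|---|---|---|
| No treatment effect (RR 1.0) | 0 | 75.0% | 83.0% | 32.9% | 10.0% |
| c = 0.1, RR 0.5 | 3.75 | 71.25/96.25 = 74.0% | 747/903.75 = 82.7% | 71.25/228 = 31.25% | 9.6% |
| c = 0.5, RR 0.5 | 18.75 | 56.25/81.25 = 69.2% | 747/918.75 = 81.3% | 56.25/228 = 24.7% | 8.1% |
| c = 0.5, RR 1.2 | −7.5 | 82.5/107.5 = 76.7% | 747/892.5 = 83.7% | 82.5/228 = 36.2% | 10.8% |

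NPV stays at 747/772 = 96.8% throughout, because trial cerclage reaches only test-positives.

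The value c = 0.1 takes FDCS women as 20% of test-positives (section 1.1 gives up to 20% of in-labour caesareans), all randomised, half to cerclage. The value c = 0.5 describes an FDCS-only group with full uptake. At RR 0.5 the losses are:
- sensitivity: 1.0 to 5.8 points (stated precision 10);
- specificity: 0.3 to 1.7 points (stated precision 3);
- PPV: 3.75/228 = 1.6 to 18.75/228 = 8.2 points (stated precision 7).

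**3. Randomised women dropped from OBS, 50% of positives.** TP 37.5, FP 76.5. Sensitivity 37.5/62.5 = 60.0%; specificity 747/823.5 = 90.7%; PPV 37.5/114 = 32.9%, unchanged; event rate 62.5/886 = 7.1%.

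**4. Primary rate (<37 weeks).** The plan gives no cerclage effect for this endpoint, so suppose the halving carries over. With FDCS at 20% of 2200 there are 440 women. At 22.8% short (228/1000) about 100 are eligible and about 50 are allocated cerclage. At an untreated risk of 10% to 32.9% in those women, 2.5 to 8.25 events are averted. That is 0.1 to 0.4 points in the whole cohort and 0.6 to 1.9 points in the FDCS group. If instead 500 of the 2200 received cerclage, the whole-cohort shift would be 500 × 0.05/2200 = 1.1 points, or 500 × (0.10/0.70) × 0.5/2200 = 1.6 points.

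**5. Does weighting repair it?** With all 228 positives randomised, the standard-care arm is expected to hold 37.5 TP and 76.5 FP. Weight 2 gives 75 and 153, which is the original table.

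**The case against.** The strongest reply is that the effect may be small or absent. Section 1.1 says cerclage may be less efficacious after FDCS, and with no effect there is no bias. Only consenting FDCS women with a short cervix are offered it and only half are allocated it. At a 20% share the losses lie well inside the stated precision. CL prediction is a secondary endpoint that depends on clinically acquired data, and interventions are already recorded. All of this stands as a limit on size and direction.

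It does not remove the gap. Section 7.3 sends FDCS women for CL surveillance, whereas section 3.1 collects CL otherwise only when clinically indicated. On that reading the CL data concentrate in the affected group and the upper figures come closer. The Professional Summary, however, says all women with an in-labour caesarean will be screened, so the actual share cannot be fixed from the documents. Nor does dilution across OBS protect the FDCS stratum in the dilatation comparison.

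A reader might also infer that every accuracy measure is certain to fall, or falls as far as 60% sensitivity and 16% PPV. Those two figures need every test-positive woman to be treated. The 1:1 allocation does not produce that, and the Lay Summary says cerclage for a short cervix is not routine care after FDCS. Nor does dropping randomised women lower everything: PPV is unchanged and specificity rises.

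**Conclusion.** The point holds as an unhandled treatment effect of conditional direction and limited size. If cerclage works, sensitivity, specificity, PPV and the FDCS-group preterm birth risk are biased downward. If it has no effect there is no bias, and if it harms the bias is upward. At the planned halving of risk only the PPV loss at the upper end exceeds its stated precision.

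The contrast between FDCS and 4-9 cm women would shrink if cerclage works. The amount depends on uptake and on the effect on delivery <37 weeks, which the plan does not give, so no single figure is supported. It would likewise go too far to conclude that the OBS primary rate is materially biased: the shift approaches or passes the 1.5-point target only if about 500 of the 2200 women receive cerclage.

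Assumptions: the <34-week halving is read as RR 0.5 and applied to test-positives; section 5's 10% event rate is used for accuracy; short cervix is equally common across dilatation groups in the 20% case; all eligible women are randomised; and there is no treatment outside the trial. The arithmetic is for CL. The effect on fetal fibronectin accuracy depends on its overlap with short cervix, which the plan does not give.

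**What to change.** In section 4.1(vi) and section 8:

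- State that women randomised in CRAFT-RCT remain in CRAFT-OBS.
- For CL and fibronectin accuracy, and for dilatation-specific risk without ultrasound-indicated cerclage, exclude the cerclage arm by allocation (not by treatment received). Give standard-care-arm women weight 2, the inverse of the 1:1 allocation, and use robust standard errors. All other women keep weight 1.
- Label the result 'risk under standard care'. It is not an untreated risk, because sections 7.1 and 7.4 permit rescue cerclage in that arm.
- Report the unweighted as-managed rate separately.
- Flag cerclage, pessary or progesterone given outside the trial. Show results without those women only as a sensitivity analysis, since removing them is itself selective.

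Interventions are already to be collected, so the change is to wording and analysis code. The price is precision. For PPV in section 5's example the 6.1-point half-width becomes about 6.7 when FDCS women are 20% of test-positives: the effective number is 228²/(182.4 + 4 × 22.8) = 190, and 6.1 × √(228/190) = 6.7. In an FDCS-only group with full uptake it becomes about 8.6 (6.1 × √2).

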4.2. CRAFT-RCT

Primary endpoint:

- i. Delivery <34 weeks gestation (powered)

Secondary endpoints:

- i. Adverse perinatal outcome, defined as composite outcome of death (ante-partum/intra-partum stillbirths plus neonatal deaths prior to discharge from neonatal services) or one/more of intraventricular haemorrhage, periventricular leukomalacia, hypoxic ischaemic encephalopathy, necrotizing enterocolitis, bronchopulmonary dysplasia and sepsis.
- ii. Gestation at delivery.
- iii. Requirement for rescue cerclage (bulging fetal membranes).
- iv. Time between intervention and delivery.
- v. Health costs at 28 days post-delivery.

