We will screen all pregnant women with a history of caesarean section in labour booked for maternity care at all participating sites with transvaginal ultrasound and quantitative fetal fibronectin (if available) between 14⁺⁰ and 23⁺⁶ weeks with a previous in labour CS. These women will be grouped into:

1. Unknown dilatation at time of CS in labour.
2. Dilated 4cm to 9cm at time of CS in labour.
3. Full dilatation at time of CS in labour.

This part of the project will allow us to:

1. Determine pregnancy outcomes in women who have had previous in-labour CS.
2. Evaluate risk of PTB/LM according to degree of dilatation in previous in-labour CS.

Study Protocol: **Cerclage After Full-dilatation caesarean-section**

IRAS ID:261294

REC: REC 19/LO/1270

Version 2.0

Date: 10.09.19

3. Evaluate the predictive value of quantitative fetal fibronectin in women with previous CS in labour if done by direct care team for clinically indicated reasons at any point
4. Evaluate the predictive value of transvaginal ultrasound and whether cervical defects can be identified if performed by direct care team for clinically indicated reasons at any point.
5. Identify women who require referral into specialist preterm surveillance clinics.
6. Identify potential participants for CRAFT-RCT (see Figure 1).

CRAFT-RCT: a trial of USS indicated cerclage in women with history of FDCS

The aim of this trial is to evaluate efficacy of cervical cerclage in pregnant women with a short cervix ($\leq 25\text{mm}$) on TVS between 14⁺⁰ and 23⁺⁶ weeks gestation following a FDCS. The study will allow us to evaluate the impact of cervical cerclage on:

1. Primary obstetric outcome – spontaneous preterm birth rate < 34 weeks gestation.
2. Secondary outcomes - Short-term pregnancy and neonatal outcomes, including a composite of neonatal death and morbidity.

CRAFT-IMG: a study evaluating imaging methods for assessing risk and management of women with a history of FDCS

This imaging sub-study will focus on analysis of TVS and magnetic resonance imaging (MRI) of cervical defects in this population to elucidate which women are at increased risk of PTB/LM. Assessment of any identified cervical defect and its relation to a cervical cerclage will also help us to establish which women at risk of PTB would benefit from this treatment.

Objectives of the imaging study:

1. To assess whether cervical abnormalities can be visualised in the cervix by TVS and MRI.

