If we have data from participants in this study of their cervical length and/or quantitative fetal fibronectin we will be able to carry out predictive statistics. This would involve calculating ROC curves for prediction of spontaneous preterm birth for both fibronectin and transvaginal cervical

length measurement as a continuous variable, for delivery <24, <30, <34 and <37 weeks gestation. From the optimal thresholds, predictive statistics will be calculated.

6. Participant inclusion and exclusion criteria

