6.2. Inclusion and exclusion criteria specific to CRAFT-RCT

Inclusion criteria:

- Pregnant women between 14⁺⁰ and 23⁺⁶ weeks gestation with a history of FDSC.
- Short cervix (≤ 25 mm) on transvaginal ultrasound scan.

Exclusion criteria:

- Women with persistent fresh vaginal bleeding evident on speculum examination.
- Women with visible fetal membranes evident on speculum examination or open cervix on ultrasound scan.
- Women with severe abdominal pain/evidence of sepsis (as judged by attending clinician).
- Known significant congenital or structural or chromosomal fetal abnormality.
- Suspected or proven rupture of the fetal membranes at the time of recruitment.

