7.1. Identification of participants

CRAFT-OBS

We will recruit pregnant women who are booked for their delivery at participating centres who provide written informed consent to participate in the study and who meet the study eligibility criteria.

Women who have previously had an emergency caesarean in labour will be identified through their booking appointment or scan appointments by the direct care midwife, doctor, sonographer and approached with information about this observational study. Clinical midwives, doctors or sonographers will highlight eligible women to the research team. The research team will then be able to discuss the research with patients if they are eligible at the time of their first trimester or second trimester scan.

CRAFT-RCT

Women participating in CRAFT-OBS will be eligible for CRAFT-RCT if they are found to have a cervix ≤ 25 mm prior to 23⁺⁶ weeks gestation with a history of FDCS. Women with a previous full dilatation caesarean section will be identified by a member of the direct care team and referred for cervical surveillance as per new guidance (1,2). The research team will check relevant hospital records when patients are consented in order to confirm a previous full dilatation caesarean section occurred. If these records are not available for review the patients will be excluded. Eligible women will be informed about the trial by a doctor, sonographer or midwife if their transvaginal ultrasound confirms a short cervix (≤ 25 mm). Members of the research team

Study Protocol: **Cerclage After Full-dilatation caesarean-section**

IRAS ID:261294

REC: REC 19/LO/1270

Version 2.0

Date: 10.09.19

(midwives, doctors and scanning practitioners) can then discuss the research further and consent women.

- If a woman is randomised to a cervical cerclage, the procedure needs to take place within 7 days of diagnosis of cervical shortening and removed around 37 weeks gestation. She will also have regular scan surveillance in accordance with local protocols. Rescue cerclage can be offered in cases of cervical opening with exposed membranes as per local guidelines. Targeted admission for bedrest and steroids can also be offered as per clinician practice and local protocols.

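### CRAFT-RCT does not say whether pregnancy losses before 24+0 weeks count in its adverse perinatal composite, and late miscarriage is not a trial endpoint although an objective names it

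*Combined protocol and SAP*

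**What the plan says.** **Entry window.** Section 6.2 admits "Pregnant women between 14⁺⁰ and 23⁺⁶ weeks gestation with a history of FDSC". Every woman is therefore randomised before 24+0.

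**Objective.** Section 2.2.2 asks whether cerclage prevents late miscarriage or preterm birth before 34 weeks.

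**Composite, three wordings.**
- Section 4.2: "defined as composite outcome of death (ante-partum/intra-partum stillbirths plus neonatal deaths prior to discharge from neonatal services", or any of six neonatal morbidities. No gestational limit is given, and stillbirth is not defined in the document.
- Section 2.2.2: "assessed as a composite of fetal and perinatal death and major morbidity".
- Professional summary: "including a composite of neonatal death and morbidity".

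**Late miscarriage.** Section 4.1 lists "Late miscarriage (14⁺⁰-23⁺⁶ weeks") for CRAFT-OBS, as an item separate from a death composite with the same stillbirth and neonatal wording. It is not among the five RCT secondary endpoints in 4.2. Section 8 says "Secondary analyses will include secondary endpoints as per section 4.2", so no comparison of late miscarriage by arm is prespecified.

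**Primary endpoint.** Section 4.2 gives delivery before 34 weeks with no lower limit, and does not say whether a late miscarriage is a delivery.

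**Neonatal follow-up.** Section 7.3 stops at discharge or 28 days, whichever is sooner, and section 3.4 ends the study on the same rule. Section 4.2 counts deaths up to discharge from neonatal services, and 7.3 also says that outcomes are collected after discharge from neonatal care.

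**The concern.** A loss before 24+0 is a competing event: it removes the fetus from risk of everything the composite counts. If it is scored as no adverse outcome, or if the pregnancy leaves the denominator, the composite compares the arms on a set of pregnancies that treatment may itself change. A cerclage that turns losses into live preterm births could look worse, and one that causes losses could look better. Either direction is plausible here: the lay summary expects many late miscarriages in this population, and section 9.5.3 lists miscarriage among the risks of cerclage.

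The primary endpoint does not fill the gap. Read literally, it scores a loss at 20 weeks and a live birth at 33 weeks alike, and the composite is where they should be told apart. The trial is open label, so a scoring rule chosen after data have been seen would be open to challenge.

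The follow-up conflict is a separate matter. A 28-day cut-off could miss deaths and morbidity in infants still in hospital at day 28.

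**Working it through.** **1. The plan's own figure.** Section 5 gives 10% against 5%, 80% power, 474 per group. Alpha is not stated; two-sided 0.05 is assumed.

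n = [1.96 × √(2 × 0.075 × 0.925) + 0.8416 × √(0.10 × 0.90 + 0.05 × 0.95)]² / 0.05² = 434.4, or 435 per group.

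With continuity correction: (434.4/4) × [1 + √(1 + 4/(434.4 × 0.05))]² = 473.6, or 474. This matches. 474/0.95 = 499, consistent with 500 per arm. No figure is stated for the composite.

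**2. Inputs for the illustration.** Only the 10% control rate and the 10% to 5% effect come from the plan. The rest is assumed:
- 40% of deliveries before 34 weeks are late losses (range 30–50%).
- 40% of live births before 34 weeks have death or a listed morbidity (30–50%).
- No composite events at 34 weeks or later (0–3%).
- 475 analysed per arm (500 × 0.95).

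**3. Formulas.** Per arm, L = loss rate, B = live births before 34 weeks, m = event rate in B, e = event rate at 34 weeks or later.
- Losses scored event-free: A = B·m + (1 − L − B)·e
- Losses dropped from the denominator: A/(1 − L)
- Losses counted: A + L

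Control arm: L = 0.04, B = 0.06, so A = 0.06 × 0.4 = 2.4%, and 6.4% with losses counted. About 475 × 0.04 = 19 control-arm losses (14 to 24 over the range) would go unscored. That is 4/6.4 = 62% of all death-or-morbidity events (33–77% over the ranges).

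**4. Scenarios** (risk ratio, cerclage against control; 95% CI on the log scale; e = 0).

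| Cerclage arm | Event-free | Dropped | Counted |
|---|---|---|---|
| (1) Half of losses become live births <34: L = 0.02, B = 0.08 | 3.2/2.4 = 1.33 (0.63–2.84) | 1.31 | 5.2/6.4 = 0.81 (0.49–1.36) |
| (2) Losses rise, live births <34 fall: L = 0.06, B = 0.04 | 1.6/2.4 = 0.67 (0.27–1.65) | 0.68 | 7.6/6.4 = 1.19 (0.75–1.89) |
| (3) Planned 10% to 5%, proportional: L = 0.02, B = 0.03 | 1.2/2.4 = 0.50 (0.18–1.36) | 0.49 | 3.2/6.4 = 0.50 (0.27–0.91) |

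**5. Sensitivity, varying all three assumptions together.**
- Scenario 1: 1.09 to 1.50 event-free, 0.73 to 0.92 counted.
- Scenario 2, with losses up by 2 points: 0.60 to about 0.87 event-free (upper end 0.042/0.048 = 0.875), 1.10 to 1.27 counted.
- Scenario 3: the two ratios are equal only at e = 0. At e = 1% they are 0.65 and 0.57, at e = 3% 0.79 and 0.66. Both stay below 1.

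If losses rise to 6% while live births before 34 weeks stay at 6%, the event-free ratio is 1.00 and the counted ratio 1.31 (0.83–2.07). The harm is missed, but no false benefit appears.

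**The case against.** **Late miscarriage is not overlooked.** It is part of objective 2.2.2, a primary endpoint without a lower limit can capture it, and gestation at delivery would show a shift before 24 weeks. The wording in 2.2.2 even points towards counting fetal losses. This stands: the gap is a mismatch between an objective and the endpoint list. It does not supply a rule for the composite or a comparison by arm.

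**Exclusion is only an inference.** A reader might conclude from the separate item in 4.1 that the composite leaves late losses out. That is a natural reading, but endpoints in that list overlap elsewhere (delivery before 34 weeks sits under a primary of delivery before 37), so separate listing proves nothing. The documents leave the question open.

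**The primary endpoint.** A reader might infer that it omits these losses and that the sample size fails, or take "for delivery <24, <30, <34 and <37 weeks gestation" in section 5 as proof that they are included. Neither follows. That phrase concerns conditional ROC analyses of fibronectin and cervical length. The literal primary endpoint includes losses, but the plan does not say so.

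**The numbers are hypothetical.** This also stands. The documents give no loss share or morbidity rate, zero late events is the assumption most favourable to a reversal (at 3%, scenario 1 shrinks to 1.16 against 0.87), and scenarios 1 and 2 hold delivery before 34 weeks at 10% in both arms.

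**The 28-day rule.** Because 7.3 also promises collection after neonatal discharge, under-counting is possible but not certain.

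**Conclusion.** The point holds as a definition gap in a secondary endpoint that should be fixed. Three wordings of the composite differ on fetal death, none settles losses before 24+0, and late miscarriage is named in an RCT objective without being an RCT endpoint.

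Under the stated assumptions, scoring losses event-free or dropping them can move the point estimate across 1 in either direction (1.33 or 1.31 against 0.81; 0.67 or 0.68 against 1.19). All those intervals span 1, so the risk is a misleading estimate. A reader might fear a significant false result, but the illustration does not show one. Under the planned proportional effect the direction does not reverse; at e = 0 the cost is precision, with about 11 against 6 events in place of 30 against 15.

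The 474/500 calculation reproduces and is not challenged, provided that the 10% and 5% rates use the same definition of delivery as the endpoint. The conflict of 7.3 and 3.4 with 4.2 is a contradiction in the text and does not depend on the illustration.

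**What to change.** **Section 4.2.** Define the composite over all randomised pregnancies so that any fetal loss after randomisation counts, alongside stillbirth, neonatal death before discharge from neonatal services and the listed morbidities. Add late miscarriage by arm as an RCT secondary endpoint. State that delivery before 34 weeks includes losses before 24+0. Bring 2.2.2 and the professional summary into line.

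**Sections 7.3 and 3.4.** Reconcile both with 4.2 so that composite outcomes are collected to neonatal discharge. Amending 7.3 alone would leave the study-end definition in conflict.

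**Minor.** Measure the time from intervention to delivery from randomisation in both arms, because the standard-care arm has no intervention date.

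**Cost.** Wording changes in five places. No new data on losses should be needed: "Women participating in CRAFT-OBS will be eligible for CRAFT-RCT", and CRAFT-OBS already lists late miscarriage. The sample size does not change. The downsides are longer record review for infants in hospital past day 28 and a slightly later study end.
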